## 12.4 Stopping Rules for Tumor Lysis Syndrome (TLS)

Besides prophylaxis and dose modification for TLS per [Section 5.9.3](#) and [Section 7.2](#), the study will implement accrual stopping rules for both clinical TLS and laboratory TLS. When a stopping rule is triggered, the study PMT will review and assess the safety of the trial and submit a report to the COH DSMC. The COH DSMC will review for approval any decision to continue or permanently suspend accrual to the trial.

### 12.4.1 Clinical TLS Stopping Rule

Study accrual will be suspended when the first incidence of clinical TLS is reported.

### 12.4.2 Laboratory TLS Stopping Rule

The incidence of laboratory TLS will be monitored with 12% being the benchmark based on IB. Operationally, the study accrual will be suspended if:

- 1 patient experiences laboratory TLS when there have been  $\leq 5$  patients treated
- 2 patients experience laboratory TLS when there have been  $\leq 14$  patients treated
- 3 patients experience laboratory TLS regardless of the number of patients treated

The rule is derived based on a  $<50\%$  probability of the rule being triggered when the true laboratory TLS incidence is  $\leq 12\%$ .

## 12.5 Statistical Analysis Methods

Patient demographics and baseline disease characteristics, including age, gender, medical history, and prior therapy, will be summarized using descriptive statistics. For continuous variables, descriptive statistics such as number, mean, standard deviation, standard error, median (range) etc. will be provided. For categorical variables, patient counts and percentages will be provided.

Rates and 95% Clopper-Pearson binomial confidence interval (CI) will be calculated for overall response rate (patients that have confirmed CR or PR), as well as for CR rate. Time to response, duration of response (only among subjects achieving CR/PR), overall survival, and progression-free survival will be estimated using the product-limit method of Kaplan- Meier with the Greenwood estimator of standard error. Median progression-free survival and overall survival and their corresponding 95% CIs will be estimated. Observed toxicities will be summarized as summary statistics in terms of type (organ affected or laboratory determination), severity, attribution, time of onset, duration, probable association with the study treatment, and reversibility of outcome.

For the exploratory objective on determining the changes in Bcl-2 gene expression in pre- and post-treatment tumor samples, summary statistics and plots will be used to describe the pre- and post-treatment gene expression levels and the associated change between the timepoints. Paired t-test or Wilcoxon signed rank test will be used to explore the difference in gene expression levels before and after treatment. Data transformation such as log transformation will be considered if appropriate. Exploratory analyses will be performed to investigate the association of the pre-/post-treatment Bcl-2 gene expressions and the change in gene expression with the clinical outcomes. For the exploratory correlation of these gene expression level/change with response, analyses comparing groups of participants defined by response may be conducted by two-sample t-test or Wilcoxon rank sum test. For the exploratory correlation of these endpoints with survival outcomes, survival analysis techniques such as Log rank test will be used. Appropriate regression models will also be considered, such as logistic regression model for

analyses on response and Cox proportional hazards models for analyses on survival outcomes. All these analyses are exploratory in nature and are intended to generate hypotheses that may be validated in larger studies; no multiple comparison adjustments will be made in these exploratory analyses.

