- d. Cycle 1 Day 1 is defined as the day of venetoclax and romidepsin initiation. Delay the Cycle 1 Day 1 dose if the participant is experiencing laboratory TLS as defined in [Appendix B](#).
- e. Assessments must be **performed and reviewed within 72 hours prior** to the C1D1 venetoclax dose (except [tumor imaging](#)).
- f. Cycle 1 Day 2-7 ( $\pm$  2 hours) laboratory assessments must be performed and reviewed prior to administration of the Cycle 1 Day 2-7 venetoclax doses.
- g. *End of protocol therapy (EOT) assessments* to be performed no later than 7 days after decision to end treatment (except tumor imaging); assessments performed after last dose of study agent and within 7 days of the decision to end treatment may serve as EOT assessments. **NOTE:** Tumor imaging performed after last dose of study agent and within 28 days of the decision to end treatment may serve as EOT imaging assessment.
- h. *Safety visit* to occur 30 (-2/+7) days post-last dose of protocol therapy. Expedited reporting will occur during this period (See [Section 7.7.2](#)). Safety follow-up may be extended until resolution/stabilization of reportable AEs.
- i. For participants yet to progress, Response Follow-up will occur every 2 months (+/- 7 days) from the day of last response evaluation until progression or the initiation of a new therapy.
- j. Participants who end Response Follow-up will enter Survival Follow-up. Survival assessment to occur bi-annually or as requested by the Study PI via medical record review, review of social security registry, or telephone call.
- k. *Informed consent* process to be fully documented (see [Section 16.4](#)). Informed consent must occur prior to any research only (non-SOC) screening procedures.
- l. *Medical history* to include a review of treatment history, any ongoing medical conditions and medical history pertaining to eligibility on study and involvement during study
- m. *Eligibility criteria* are detailed in [Section 3.0](#).
- n. *Registration* into a COH clinical trial management system (CTMS).
- o. *Standard physical exam* includes weight and skin analysis.
- p. *Vital signs*: heart rate, blood pressure, respiration rate, and temperature.
- q. *Concurrent medications* and reason for administration to be documented from within 10 days prior to protocol therapy up to 30-days-post last dose visit. See [Section 5.9](#) for concomitant medication restrictions and guidelines.

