**Table 11.3. Clinical Endpoints**

Endpoint	Patients	Definition
Overall response rate (ORR)	Evaluable patients	Proportion of patients achieving CR or PR
Complete response (CR) rate	Evaluable patients	Proportion of patients achieving CR
Time to response	Evaluable patients	Date of initiation of protocol treatment to date when criteria for response (PR or CR) is first met
Duration of response (DOR)	CR and PR only	Date when criteria for response (CR or PR) is first met until date criteria for PD or relapse is first met
Progression free survival (PFS)	Evaluable patients	Date of initiation of protocol treatment to date criteria for PD is first met or death as a result of any cause
Overall survival (OS)	Evaluable patients	Date of initiation of protocol treatment to date of death from any cause

**Note:** Evaluable patients are patients evaluable for response, as defined in [Section 12.3](#).

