### 12.1 Statistical Design

This is a multi-institution, single arm Phase 2 trial to evaluate the anti-tumor activity and safety/tolerability of venetoclax with romidepsin in patients with relapsed/refractory mature T-cell lymphoma. Patients will take oral venetoclax daily and romidepsin on days 1, 8, and 15 of each cycle for up to 26 cycles (28-day cycle) Response will be assessed after every 2 cycles until disease relapse/progression. Patients will be followed for 24 months after the end of protocol treatment. The primary endpoint is overall response rate. Secondary endpoints include toxicities, CR rate, duration of response, time to response, PFS, and OS. The study will accrue up to 18 evaluable patients for the primary response endpoint evaluation. The first 6 patients enrolled on the study will be part of a Safety Lead-in to evaluate the safety and tolerability of the proposed dose of venetoclax with romidepsin as described below in [Section 12.1.1](#).

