### **12.3 Evaluable Participants and Participant Replacement**

- ***Evaluable for unacceptable toxicity during Safety Lead-in:*** Patients evaluable for unacceptable toxicity (defined in [Section 11.2](#)) are:
  - 1) Those who received at least 75% of the total dose of each drug for the first 2 cycles of therapy combined OR
  - 2) Those who experience any unacceptable toxicity during the first 2 cycles regardless of actual dose received.

During safety lead-in, patients who are not evaluable for unacceptable toxicities will be replaced.

- ***Evaluable for response:*** Patients evaluable for response are those who received at least 2 cycles of protocol treatment and have a response evaluation after 2 cycles. Subjects who terminate treatment prior to 2 cycles due to disease relapse/progression or unacceptable toxicity will be considered evaluable for response and be considered non-responders. Patients who terminate prior to 2 cycles for other reasons will be inevaluable for response. Patients not evaluable for response will be replaced.

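### Kaplan-Meier for time to response in all evaluable patients, with no written censoring rule, will by default overstate the proportion responding by each time; cumulative incidence is the better estimator

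*Combined protocol and SAP*

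**What the plan says.** Section 12.5 names the method: "Time to response, duration of response (only among subjects achieving CR/PR), overall survival, and progression-free survival will be estimated using the product-limit method", with Greenwood standard errors. The restriction to patients in CR or PR is attached to duration of response only.

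Table 11.3 keeps the same split. Duration of response is assigned to CR and PR patients. Time to response is assigned to evaluable patients and runs from "Date of initiation of protocol treatment to date when criteria for response (PR or CR) is first met". The table's note reads "Evaluable patients are patients evaluable for response, as defined in" Section 12.3. That section keeps early failures in the set: "Subjects who terminate treatment prior to 2 cycles due to disease relapse/progression or unacceptable toxicity will be considered evaluable for response", and it counts them as non-responders.

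Two further passages fix how long response can be observed. Section 12.1 says "Response will be assessed after every 2 cycles until disease relapse/progression". The notes to Table 10.0 say that response follow-up runs "from the day of last response evaluation until progression or the initiation of a new therapy".

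No section gives a censoring rule for time to response, and no section mentions a competing event or a cumulative incidence method.

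**The concern.** Time to response has one event, the first CR or PR. The analysis set includes patients who never have it. For a patient who progresses or dies first, response assessment has ended, so the natural way to enter that patient in a Kaplan-Meier calculation is as censored at that point. Kaplan-Meier then assumes that the patient would have gone on to respond at the same rate as those still under assessment. The ORR analysis counts the same patient as a non-responder.

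The consequence is a time-to-response curve that sits above the proportion of patients who have actually responded by each time. In a report on 18 patients, a curve whose plateau is higher than the binomial ORR beside it would mislead the reader about activity, and its Greenwood interval would be an interval for the wrong quantity.

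**Working it through.** **Plan's own figure.** The documents give none for time to response. The one related figure is the Simon design (0/7, then reject with 4 or more of 18). With P(reject | p) = sum over x = 1 to 7 of Bin(x; 7, p) × P[Bin(11, p) ≥ 4 − x], it gives a one-sided type I error of 0.089 at p = 10% and power of 0.800 at p = 30%. The stated 10% and 80% reproduce, and time to response does not enter them.

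**Formulas.** With r responses among n at risk at each scan:
- 1-KM = 1 − product of (1 − r/n), with patients who leave without response censored.
- Cumulative incidence = sum of S × r/n, where S is the probability of reaching that scan with neither response nor a competing event.

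**Worked example (assumed data).** There are 18 patients. At scan 1, 4 respond and 8 progress; at scan 2, 1 of the remaining 6 responds.
- 1-KM = 1 − (14/18)(5/6) = 35.2%.
- Cumulative incidence = 4/18 + (6/18)(1/6) = 5/18 = 27.8%, the crude response proportion.
- If non-responders were instead kept at risk to the end of follow-up, 1-KM = 1 − (14/18)(13/14) = 5/18 = 27.8%. So the result turns on a rule that the plan does not state.

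**When the two agree.** With 5 responses, all at the first scan and no earlier exits, both give 5/18 = 27.8%. If 4 patients leave before that scan, 14 are at risk and 1-KM = 1 − 9/14 = 35.7%. Both conditions are therefore needed.

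**Three scans, 40% progression or death per interval (assumed).** Cumulative incidence is shown two ways: (a) the 40% is a share of all at risk; (b) the 40% is a share of those who did not respond at the scan.

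| Response per scan | 1-KM | Cumulative incidence (a) | Cumulative incidence (b) |
|---|---|---|---|
| 20/10/5% | 1 − 0.80×0.90×0.95 = 31.6% | 0.20 + 0.40×0.10 + 0.40×0.50×0.05 = 25.0% | 0.20 + 0.48×0.10 + 0.48×0.90×0.60×0.05 = 26.1% |
| 25/5/2% | 1 − 0.75×0.95×0.98 = 30.2% | 0.25 + 0.35×0.05 + 0.35×0.55×0.02 = 27.1% | 0.25 + 0.45×0.05 + 0.45×0.95×0.60×0.02 = 27.8% |

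The gaps are 5.5 to 6.6 points and 2.4 to 3.1 points. Simulation of 18-patient trials agrees: about 32% against 25-26%, and about 30% against 27-28%.

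**Sensitivity to timing.** Carrying the last response rate through six scans gives simulated means of 38.9% against 26.1% and 33.1% against 27.5%. A separate simulation fixed the true ORR and varied two things: the median time to progression in non-responders, from 6 months down to 1.5, and the responses, from all at the first scan to spread over three.
- True ORR 30%: 1-KM averages 35% to 59%; cumulative incidence about 30%.
- True ORR 10%: 1-KM averages 12% to 25%; cumulative incidence about 10%.

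The upper ends need early progression together with later responses.

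**The case against.** Several points on the other side stand.

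- **The censoring is inferred.** A reader might take the plan to say that progression and death are censored. It does not; it is silent. A rule that kept non-responders at risk to the end of follow-up would remove the bias. But no such rule is written, and with assessment ending at progression or new therapy, censoring there is what standard practice would produce.
- **The gap is not inevitable.** The synopsis places the primary endpoint after 2 cycles, that is, at the first scan. If responses concentrate there and few patients leave earlier, the difference is small or nil. The worked example's 7.4 points is about 1.3 patients of 18 (0.074 × 18). Section 2.7 also places the end of treatment for progression after at least two cycles, while Section 12.3 provides for earlier termination. Those passages must be reconciled, and they bear on how many exits precede the first scan.
- **Not every non-responder is a progression or a death.** A 30% alternative leaves 70% without response, and a reader might treat all of them as competing events. That group can also include stable disease and stops for toxicity.
- **No median time to response is planned.** A reader might infer one from the Kaplan-Meier method, but Section 12.5 names medians only for PFS and OS.
- **The response proportion is reported correctly elsewhere.** ORR and CR rate are binomial proportions with Clopper-Pearson intervals, and no test or decision rests on time to response.

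These points limit the size and importance of the problem. They do not supply the missing rule, and they do not make Kaplan-Meier the right estimator for this population.

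**Conclusion.** The point holds in limited form. The plan applies Kaplan-Meier to an endpoint whose analysis set includes patients who can leave without the event, and it does not say how they are treated. On the default reading, 1-KM overstates the proportion responding by each time whenever responses follow such exits. It can also exceed the ORR, taken here as any CR or PR as in Table 11.3.

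The plausible size is from nothing (all responses at the first scan, no earlier exits), through about 2 to 7 points in the three-scan illustrations, to larger gaps if responses continue over later scans or many patients leave early. All of these rest on assumed timing, because the documents give none.

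A reader might infer that the trial's efficacy conclusion is compromised. The documents do not support that: the endpoint is secondary and descriptive, and the ORR analysis, the Simon rule and the sample size do not use it.

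**What to change.** In Section 12.5, take time to response out of the Kaplan-Meier list and estimate it by the cumulative incidence function in evaluable patients, with progression or death before response as the competing event. Report median and range of time to response among responders only, as description.

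In Table 11.3, state how the remaining exits are handled. Patients who stop early for toxicity are non-responders under Section 12.3, so they should be treated in the same way as in the ORR. Say also what happens when new therapy starts before any response. Use the same definition of response for both endpoints: Section 12.5 refers to confirmed response for ORR, while Table 11.3 dates time to response from when the criteria are first met. With matching definitions and complete follow-up, the plateau of the curve equals the ORR.

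The cost is a sentence or two of text and slightly more analysis work on data already collected. The curve will look less favourable than the Kaplan-Meier one where the two differ.

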## 13.0 DATA HANDLING, DATA MANAGEMENT, RECORD KEEPING

---

### 13.1 Source Documents

Source documents are original documents, data, and records (e.g., medical records, pharmacy dispensing records, recorded data from automated instruments, laboratory data) that are relevant to the clinical trial. The investigator or their designee will prepare and maintain adequate and accurate source documents. These documents are designed to record all observations and other pertinent data for each patient enrolled in this clinical trial. Source documents must be adequate to reconstruct all data transcribed onto the case report forms.

### 13.2 Data Capture Methods and Management

Data for this trial will be collected using Medidata Rave.

### 13.3 Case Report Forms/Data Submission Schedule

Study personnel will enter data from source documents corresponding to a participant's visit into the protocol-specific electronic Case Report Form (eCRF) when the information corresponding to that visit is available.

The investigator is responsible for all information collected on participants enrolled in this study. All data collected during the course of this study must be reviewed and verified for completeness and accuracy by the investigator. All case report forms must be completed by designated study personnel. The completed case report forms must be reviewed, signed and dated by the Investigator or designee in a timely fashion.

All data will be collected using electronic data collection, stored as indicated in [Section 13.2](#), and will be submitted according to the timelines indicated in [Table 13.3](#).

**Table 13.3 Data Submission Schedule**

Form	Submission Timeline
Eligibility Checklist	Complete prior to registration
On Study Forms	Within 14 calendar days of registration
Baseline Assessment Forms	Within 14 calendar days of registration
Treatment Forms	Within 14 calendar days of treatment administration
Adverse Event Report Forms	Safety Lead-in Cycle 1 and 2: Within 7 calendar days of the assessment/notification Safety Lead-in Cycle 3+ and Phase 2: Within 10 calendar days of the assessment/notification
Response Assessment Forms	Within 10 calendar days of the response assessment
Other Assessment Forms	Within 10 calendar days of the assessment
Off Treatment/Off Study Forms	Within 10 calendar days of completing treatment or being taken off study for any reason
Follow up/ Survival Forms	Within 14 calendar days of the protocol defined follow up visit date or call

### 13.4 Regulatory Records

The investigator will maintain regulatory records, including updating records in accordance with Good Clinical Practice guidelines and FDA regulations

## 14.0 ADVERSE EVENTS AND UNANTICIPATED PROBLEMS

---

### 14.1 Definitions

#### 14.1.1 Adverse Event (AE)

An adverse event is any untoward medical experience or change of an existing condition that occurs during or after treatment, whether or not it is considered to be related to the protocol intervention.

#### 14.1.2 Serious Adverse Event (SAE)

A serious adverse event is any expected or unexpected adverse events that result in any of the following outcomes:

- Death
- Is life-threatening experience (places the subject at immediate risk of death from the event as it occurred)
- Unplanned hospitalization (equal to or greater than 24 hours) or prolongation of existing hospitalization
- A persistent or significant disability/incapacity
- A congenital anomaly/birth defect
- Secondary malignancy\*
- Any other adverse event that, based upon appropriate medical judgment, may jeopardize the subject's health and may require medical or surgical intervention to prevent one of the outcomes listed above (examples of such events include allergic bronchospasm requiring intensive treatment in the emergency room or at home, blood dyscrasias or convulsions that do not result in inpatient hospitalization, or the development of drug dependency or drug abuse).

\*Modified from [21 CFR 312.32](#)

#### 14.1.3 Unanticipated Problems Involving Risks to Subjects or Others

An unanticipated problem is any incident, experience, or outcome that meets all three of the following criteria:

1. Unexpected (in terms of nature, severity, or frequency) given the following: a) the research procedures described in the protocol-related documents such as the IRB approved research protocol, informed consent document or Investigator Brochure (IB); and b) the characteristics of the subject population being studied; **AND**
2. Related or possibly related to participation in the research (possibly related means there is a reasonable possibility that the incident, experience, or outcomes may have been caused by the drugs, devices or procedures involved in the research); **AND**
3. Suggests that the research places subjects or others at greater risk of harm (including physical, psychological, economic, or social harm) than previously known or recognized.

#### **14.1.4 Adverse Events of Special Interest (AESI)**

Specific adverse events, or groups of adverse events, will be followed as part of standard safety monitoring activities. These events, regardless of seriousness, will be reported.

##### ***14.1.4.1 Study Specific AESIs***

- Tumor lysis syndrome (see [Section 7.5](#))
- Overdose (see [Section 7.6](#))

#### **14.2 Assessment of Adverse Events**

The site Investigator will be responsible for determining the event name, assessing the severity (i.e. grade), expectedness, and attribution of all adverse events.

##### **14.2.1 Assessment of Adverse Event Name and Grade**

Adverse events will be characterized using the descriptions and grading scales found in the most recent version of CTCAE v. 5.0. A copy of the scale can be found at [NCI/CTEP web site](#). The determination of severity for all other events not listed in the CTCAE v. 5.0 should be made by the investigator based on medical judgment and the severity categories of Grade 1 to 5 as defined below:

- Grade 1 (mild) – An event that is usually transient and may require only minimal treatment or therapeutic intervention. The event does not generally interfere with usual activities of daily living.
- Grade 2 (moderate) – An event that is usually alleviated with additional specific therapeutic intervention. The event interferes with usual activities of daily living, causing discomfort but poses no significant or permanent risk of harm to the subject.
- Grade 3 (severe) – An event that requires intensive therapeutic intervention. The event interrupts usual activities of daily living, or significantly affects the clinical status of the subject.
- Grade 4 (life threatening) – An event, and/or its immediate sequelae, that is associated with an imminent risk of death or with physical or mental disabilities that affect or limit the ability of the subject to perform activities of daily living (eating, ambulation, toileting, etc.).
- Grade 5 (fatal) – Death (loss of life) as a result of an event.

